### 9.1.2 Sensitivity Analyses

Sensitivity analyses based on different missing data imputation rules will be conducted for the primary endpoint. Specific imputation rules are:

1. Completers Analysis (Week 8 Observed) Data Imputation
  - Subjects who do not complete the Week 8 Visit will be imputed as missing
  - Subjects who demonstrate corneal healing at Week 8 and are missing Week 10 data will be imputed as missing at Week 8
2. LOCF Data Imputation
  - Subjects with missing Week 8 and/or Week 10 data will have their last observed data carried forward
3. Tipping point analyses will be performed.
  - In CSB-001 arm, one responder will be changed to be a non-responder, and the same primary analysis will be performed. In CSB-001 arm, two responders will be changed to be non-responders, and the same primary analysis will be performed again. This will continue until X responders in CSB-001 arm are changed to be non-responders when p-value becomes not statistically significant. In these analyses, no changes will be made to the vehicle arm.
  - In the vehicle arm, one non-responder will be changed to be a responder, and the same primary analysis will be performed. In the vehicle arm, two non-responders will be changed to be responders, and the same primary analysis will be performed again. This will continue until X non-responders in the vehicle arm are changed to be responders when p-value becomes not statistically significant. In these analyses, no changes will be made to the CSB-001 arm.

In addition, instead of Chi-squared test, Cochran–Mantel–Haenszel (CMH) test stratified by stage 2 NK vs stage 3 NK will be used to analyze the primary endpoint as another sensitivity analysis.

Per-protocol analysis set will also be used to analyze the primary endpoint as exploratory analyses.

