  - Subjects with corneal healing at Week 8 as assessed by the investigator will return at Week 10 for assessment of sustained healing. Schedule the subject for the next follow-up study visit (Week 10 Visit).
  - Subjects with incomplete corneal healing at Week 8 as assessed by the investigator will be unmasked. Sites will be provided instructions to unmask the subject using the IMB CD system.
    - Subjects randomized to vehicle will be eligible per investigator discretion to enter the uncontrolled treatment phase and receive 8-week treatment with CSB-001. See Section 6.2.
    - Subjects randomized to CSB-001 will exit the study and be treated per investigator discretion. See Section 6.3 for the study procedures required to be completed at the time of study exit.

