### **2.2 Study Endpoints**

For the primary efficacy endpoint, complete corneal healing is defined as absence of corneal staining in the area of the defect/ulcer (i.e., 0 mm lesion) at Week 8 and the absence of the

---

corneal staining in the area of the defect/ulcer (i.e., 0 mm lesion) two weeks later at Week 10 as assessed by a central reading center.

For the secondary endpoints, cornea healing is defined as absence of corneal staining in the area of the defect/ulcer (i.e., 0 mm lesion) at any single timepoint.

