## 9.0 EFFICACY EVALUATION

### 9.1 Primary Efficacy Endpoint

#### 9.1.1 Primary Analyses

Analyses of the primary efficacy endpoint will follow the estimand framework stated in [Section 2.2.1](#). Full analysis set will be used for the efficacy analyses.

The primary efficacy endpoint is the proportion of subjects achieving complete corneal healing defined as absence of corneal staining in the area of the defect/ulcer (i.e., 0 mm lesion) at Week 8 and the absence of corneal staining in the area of the defect/ulcer (i.e., 0 mm lesion) two weeks later at Week 10 as assessed by a central reading center.

Chi-squared test will be used to compare each CSB-001 active treatment group (QID) to vehicle. The proportion and associated 95% confidence interval will be reported by each treatment arm. Difference in the proportions between treatment arms and associated 95% confidence interval will also be reported.

Missing data of the primary efficacy endpoint will be imputed as follow:

- Subjects with missing Week 8 data for any reason will be imputed as non-responders
- Subjects who demonstrate corneal healing at Week 8 and are missing Week 10 data will be imputed as non-responders

---

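### The LOCF and completers sensitivity analyses do not estimate each arm's sustained-healing rate: LOCF can credit transient healing as sustained, and completers understates the rate in each arm

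*SAP*

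**What the plan says.** SAP 2.2 sets a two-visit endpoint: "complete corneal healing is defined as absence of corneal staining in the area of the defect/ulcer (i.e., 0 mm lesion) at Week 8", with the same finding "two weeks later at Week 10 as assessed by a central reading center" (the latter as worded in SAP 9.1.1). Protocol 6.1.9 ends dosing before the Week 8 ophthalmic assessments, so Week 10 is the only scheduled reading taken after a period off treatment.

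In the primary analysis (SAP 9.1.1) a missing Week 8 counts as failure, and for Week 10: "Subjects who demonstrate corneal healing at Week 8 and are missing Week 10 data will be imputed as non-responders".

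SAP 9.1.2 then gives two alternative missing-data rules, both also in Protocol 13.3.1:

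- Completers, first part: "Subjects who do not complete the Week 8 Visit will be imputed as missing". Second part: "Subjects who demonstrate corneal healing at Week 8 and are missing Week 10 data will be imputed as missing at Week 8".
- LOCF: "Subjects with missing Week 8 and/or Week 10 data will have their last observed data carried forward". There is no exception for the two-visit definition.

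The SAP adds: "Tipping point analyses will be performed". That analysis switches responders in the CSB-001 arm, or non-responders in the vehicle arm, one at a time until significance is lost.

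The investigator, not the CRC, decides who continues to Week 10. Protocol 6.1.9 states: "Subjects with incomplete corneal healing at Week 8 as assessed by the investigator will be unmasked". Those subjects either exit or, if on vehicle, may enter the open-label phase.

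**The concern.** A sensitivity analysis for missing data should estimate the same quantity as the primary analysis under a different, plausible assumption about the unseen outcomes. Neither rule does this for the arm-level rate.

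LOCF assumes that healing persists, which is exactly what the Week 10 reading is there to test. A Week 8 healer with no Week 10 image becomes a sustained responder. So does a subject who dropped out earlier with a healed last image.

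The completers rule keeps Week 8 failures, correctly, because their outcome is already determined. But it takes healers with no Week 10 image out of both numerator and denominator and does not reweight the healers who were seen. Failures are therefore over-represented.

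At stake is how the robustness of the primary result is read. Apart from the tipping-point exercise, these are the only planned analyses that treat missing outcomes differently from the primary rule. The CMH, per-protocol and ITT analyses do not change the imputation.

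**Working it through.** **The plan's own figures.** SAP 5.0 assumes 60% vs 30% with 48 per arm for 80% power at two-sided 0.05. The standard formula gives 42 per arm without continuity correction and 49 with it. Exact power at 48 per arm is 80.0% for the corrected test and 85.4% for the uncorrected one, so the stated size is reproduced to within one subject by the corrected test. Randomizing 128 to complete 96 allows for 1 − 96/128 = 25% loss. After 10% dropout, 1 − 0.75/0.90 = 16.7% remains for inadequate images. Missing readings are thus expected on a material scale.

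**Notation.** H = healed at Week 8 per CRC; s = sustained at Week 10 given healed at Week 8; m = Week 10 missing given healed at Week 8; d = Week 8 missing; h = last image healed among those missing Week 8. The target is H × s. The documents do not give s, m, d or h, so all are assumptions: s 0.75–0.95, m 0.10–0.25, d 0–0.10, h = H unless stated.

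**Formulas, with missingness unrelated to outcome.**

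- Completers = H s (1 − m) / (1 − H m), which is the target times (1 − m)/(1 − H m). The factor is below 1 whenever m > 0 and H < 1.
- LOCF = (1 − d) H [(1 − m) s + m] + d h.

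**Count example (assumed, 64 in an arm).** 45 are healed at Week 8, 9 of them lack Week 10, 31 of the 36 seen are sustained, and 19 are not healed.

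| Rule | Calculation | Rate |
|---|---|---|
| Non-responder | 31/64 | 48.4% |
| Completers | 31/55 | 56.4% |
| LOCF | 40/64 | 62.5% |
| Target H × s | 45/64 × 31/36 | 60.5% |

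**Design case, true 60% vs 30%, equal missingness and equal s.** Over the assumed ranges:

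| Rule | CSB-001 | Vehicle | Difference (points) |
|---|---|---|---|
| Completers | 53–59% | 24–28% | 29.0–31.2 |
| LOCF | 60–67% | 30–33% | 30.2–33.2 |

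A single worked point: assume 6% of images are unreadable and 5% of CRC-healed eyes are called not healed by the investigator. Then m = 1 − 0.94 × 0.95 = 0.107. With s = 0.85, H is 0.706 and 0.353, and completers gives 0.60 × 0.893/(1 − 0.706 × 0.107) = 58.0% and 0.30 × 0.893/(1 − 0.353 × 0.107) = 27.8%. The difference is 30.1 points from unrounded values.

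**More transient healing on CSB-001, no sustained benefit.** Assume H = 0.60 vs 0.35 and a sustained rate of 30% in both arms, so s = 0.50 vs 0.857. At m = 0.167 and d = 0.10:

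- CSB-001: 0.9 × 0.60 × (0.833 × 0.50 + 0.167) + 0.10 × 0.60 = 37.5%
- Vehicle: 0.9 × 0.35 × (0.833 × 0.857 + 0.167) + 0.10 × 0.35 = 31.3%

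This is a false difference of 6.3 points. Over m and d the range is 2.5 to 8.1 points. If no early dropout had a healed last image (h = 0), the lowest value is 29.7% − 27.5% = 2.3 points. Completers is off by only 0.7 to 1.8 points here.

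**Unequal Week 10 missingness.** Assume a true 45% in both arms, s = 0.85 (H = 0.529), d = 0.10, and m = 0.10 vs 0.25. Completers gives 0.45 × 0.90/(1 − 0.529 × 0.10) = 42.8% and 0.45 × 0.75/(1 − 0.529 × 0.25) = 38.9%. That is a false 3.9 points toward the arm with less missingness. LOCF is off by 1.1 points the other way.

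**Could missingness differ by arm?** An eye that the CRC reads as healed and the investigator as not healed has no routine Week 10 visit. Protocol 6.1.10 lets the sponsor recall such a subject, but only one who has not entered the open-label phase, and only vehicle subjects can enter it. Unequal missingness is therefore possible by design. Its size cannot be known from the documents.

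**Does the tipping point cover this?** Under the primary rule every CSB-001 responder has both readings observed, so switching them alters no missing outcome. The vehicle branch may switch observed failures and does not stop at the number missing.

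**The case against.** The estimand in SAP 2.2.1 is a difference in proportions, and in the design case both rules nearly recover it. Simulations with 10% dropout, 6% unreadable images and 5% discordance put LOCF at about 29 to 30 points and completers at about 30, against a true 30. The non-responder rule gives about 23 (45.4% vs 22.7%). A reader might infer that neither analysis can say anything about the primary result. The documents do not support that: when the arms are alike in missingness and durability, both show how far the primary rule attenuates the difference.

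Other stronger readings also fail:

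- *Completers deletes only healers.* Its first part removes everyone without a Week 8 visit, whatever their status. The selective removal is confined to subjects with Week 8 data.
- *LOCF would produce a false positive.* The transient-healing case needs half of CSB-001 healers to relapse within two weeks against 14% on vehicle, and nothing in the documents suggests this. Even then, a reported 32.8% vs 28.8% (one simulated result, 4.0 points) at 64 per arm has a standard error of about 8 points and would reach significance about 8% of the time, against 5% with no difference.
- *Discordant eyes are never imaged at Week 10.* Recall is permitted, and Protocol 7.14 makes the investigator check the images before recording an eye as not healed, which should limit discordance.

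What stands against the objection is that it relies on equal missingness and equal durability. A sensitivity analysis should not need those to hold, and the arm-level rates, which the plan will report with confidence intervals, are off even when they do.

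**Conclusion.** The point holds as a fault in two sensitivity analyses. LOCF credits unobserved durability, and completers understates each arm's rate by the factor (1 − m)/(1 − H m). The treatment difference stays within about 3 points of the truth when the arms are alike. It moves by roughly 2 to 8 points under LOCF if healing is more transient in one arm, and by about 4 points under completers if Week 10 missingness is 10% vs 25%. All these sizes rest on assumed values of s, m, d and h. The primary test, its non-responder rule and the sample size do not depend on either analysis. The change is worth making because the tipping-point analysis is not restricted to missing outcomes and so does not supply the missing check.

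**What to change.** Keep non-responder imputation as primary. In SAP 9.1.2:

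1. Replace the completers rate with (observed Week 8 CRC healing rate) × (observed Week 10 CRC healing rate among Week 8 healers), by arm, with a bootstrap interval for the difference. When missingness is unrelated to outcome, or depends only on Week 8 status once Week 8 is read, this returns H × s.
2. Replace LOCF with two-step multiple imputation, separately by arm. First impute Week 8 CRC healing from NK stage, baseline and latest CRC lesion size, and the investigator's call. Then impute Week 10 only among those healed at Week 8. Combine the risk differences by Rubin's rules.
3. State one handling of subjects read as healed by the CRC but not by the investigator who have no Week 10 image, and use it in both analyses. The choice matters. With 5% of healers discordant, counting them as failures targets 0.95 × 60% = 57.0% vs 0.95 × 30% = 28.5%, a difference of 28.5 points; treating them as missing targets 60% vs 30%.

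The Protocol 13.3.1 wording should follow, or the SAP should record the departure. The cost is SAP text and some programming on data already scheduled for collection. The downside is a model-based sensitivity analysis that is harder to explain than LOCF.

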#### **4.0 RANDOMIZATION AND BLINDING**

This is a multi-center, randomized, double-masked, vehicle-controlled, parallel-group safety and efficacy study. Approximately 128 subjects (64 per treatment arm) will be randomized in the study to complete approximately 96 subjects (48 per treatment arm).

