#### **5.0 SAMPLE SIZE CONSIDERATIONS**

With the assumption that the proportion of subjects that will achieve complete corneal healing for the CSB-001 and vehicle are 60% and 30%, respectively, 48 subjects per arm (a total of 96 subjects) will have 80% power to detect the difference of 30% at a two-sided alpha 0.05 based on a Chi-squared test. With a predicted dropout rate of ~10% and the risk of inadequate numbers of corneal defect images for interpretation by the central reading center at key visits (Day 0, Week 8, and Week 10), approximately 128 subjects will be randomized at 1:1 ratio (CSB-001: vehicle).

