## 9.2 Secondary Efficacy Endpoints

### Key secondary endpoints

- 
- Proportion of subjects achieving corneal healing at Week 8 assessed by the CRC
  - Proportion of subjects achieving corneal healing at Week 4 assessed by the CRC
  - Time to corneal healing based on assessments by the CRC
  - Time to  $\geq 20\%$  decrease in lesion size (maximum diameter) from baseline assessed by the CRC
  - Proportion of subjects achieving corneal healing at each of Week 4, and Week 8 sustained for two weeks until Week 10 assessed by the investigator
  - Proportion of subjects without persistent corneal staining during the study as assessed by the CRC
  - Proportion of subjects with complete corneal healing and without persistent corneal staining during the study as assessed by the CRC

The two time-to-event key secondary endpoints will be analyzed by a log-rank test at a two-sided alpha 0.05. Time associated with each treatment arm will be summarized using the Kaplan-Meier method and displayed graphically where appropriate. Confidence intervals (CIs) for the 25th, 50th and 75th percentiles will be reported by each treatment arm.

The two dichotomous key secondary endpoints will be analyzed using a Chi-squared test as in the analyses of the primary endpoint. The proportion and associated 95% confidence interval will be reported by each treatment arm.

Tipping point analyses will also be performed for the proportion of subjects achieving corneal healing at Week 8 assessed by the CRC.

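### The tipping-point analysis in SAP 9.1.2 is a fragility count on the final 2x2 table: it is listed as a missing-data sensitivity analysis but is not tied to the outcomes that were imputed

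*SAP*

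**What the plan says.** SAP 9.1.1 counts as a non-responder every subject with missing Week 8 data, and every subject healed at Week 8 with missing Week 10 data. SAP 2.2.1 repeats this in the estimand.

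SAP 9.1.2 opens with "Sensitivity analyses based on different missing data imputation rules will be conducted for the primary endpoint" and numbers three: a completers analysis, LOCF, and the tipping point. The tipping point has two halves:

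- CSB-001 arm: "In CSB-001 arm, one responder will be changed to be a non-responder, and the same primary analysis will be performed". Then two responders are changed, and so on until the result is no longer significant after X changes. Vehicle is held fixed.
- Vehicle arm: non-responders are changed to responders one at a time in the same way. CSB-001 is held fixed.

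The steps speak only of responders and non-responders. They do not mention subjects with missing outcomes, set a ceiling at the number missing, or ask for X to be set against that number.

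SAP 9.2 reuses the method for a key secondary endpoint: "Tipping point analyses will also be performed for the proportion of subjects achieving corneal healing at Week 8 assessed by the CRC". SAP 7.4 says that, outside the primary endpoint, nothing is imputed except partial or missing dates. The tipping point is not in the protocol's list of sensitivity analyses (Protocol 13.3.1); the SAP adds it.

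**The concern.** A missing-data tipping point asks how far the unobserved outcomes would have to depart from the imputation rule before the conclusion changes. Its answer should depend on how many outcomes were unobserved in each arm. The procedure in item 3 uses only the responder counts and denominators of the finished table, which makes it a fragility count.

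The two halves differ. Under the non-responder rule no CSB-001 responder can be an imputed one: each was read as healed by the CRC at both Week 8 and Week 10. Changing them tests no missing-data assumption. Vehicle non-responders are a mixture of observed and imputed subjects, so that half is relevant to missing data, but the SAP does not separate the two groups.

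What is at stake is a statement in the study report. A count X from an item headed as missing-data sensitivity will be read as robustness to missing data, when the same X can go with a conclusion that missing outcomes cannot overturn or with one that they easily could. The primary test and estimate are not affected.

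**Working it through.** **Inputs from the SAP.** Section 5.0: 60% v 30% healing, 48 per arm, "80% power to detect the difference of 30% at a two-sided alpha 0.05 based on a Chi-squared test", 128 randomized 1:1 (64 per arm), with a "predicted dropout rate of ~10% and the risk of inadequate numbers of corneal defect images" given as the reason for the excess. Section 4.0: about 96 of the 128 are planned to complete.

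**The plan's own figure.** Exact enumeration over all tables with 48 per arm at 60% v 30% gives power 80.0% for the continuity-corrected chi-squared test and 85.4% for the uncorrected one. The stated 80% is reproduced with the correction. The SAP does not say which version will be used, so both are shown for X. For the excess: 96/0.90 = 106.7, so 107 would cover 10% dropout; 128 implies a loss of 1 − 96/128 = 25%, or 16 per arm.

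**Formula.** With a (CSB-001) and b (vehicle) responders out of 64 per arm, the uncorrected statistic is χ² = 128(a − b)² / [(a + b)(128 − a − b)]. The correction replaces |a − b| by |a − b| − 1. The 5% critical value is 3.841.

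**Step 1: the SAP procedure on an assumed table, 38/64 v 19/64 (59% v 30%).**

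| Table | χ² (uncorrected) | p |
|---|---|---|
| 38 v 19 | 128×19²/(57×71) = 11.42 | 0.0007 |
| 30 v 19 (8 CSB-001 flips) | 128×11²/(49×79) = 4.00 | 0.045 |
| 29 v 19 (9 CSB-001 flips) | 128×10²/(48×80) = 3.33 | 0.068 |
| 38 v 26 (7 vehicle flips) | 128×12²/(64×64) = 4.50 | 0.034 |
| 38 v 27 (8 vehicle flips) | 128×11²/(65×63) = 3.78 | 0.052 |

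So X = 9 (CSB-001) and 8 (vehicle); with continuity correction, 8 and 7. The number of missing subjects enters nowhere.

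**Step 2: the same table, changing only missing subjects.** Assume m missing per arm, all currently counted as non-responders. Let i of the CSB-001 and j of the vehicle missing subjects be responders (0 to m each), and retest (38 + i)/64 v (19 + j)/64, uncorrected. The worst case is i = 0, j = m.

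| m per arm | Worst-case p | Combinations losing significance |
|---|---|---|
| 0 | 0.0007 | 0 of 1 |
| 3 | 0.0046 | 0 of 16 |
| 6 | 0.022 | 0 of 49 |
| 8 | 0.052 | 1 of 81 |
| 16 | 0.59 | 40 of 289 |

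One table and one pair of X values thus go with opposite answers about missing data.

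**Step 3: a table that already reflects heavy missingness.** If 16 per arm are missing and 60% v 30% holds among the other 48, the counts are 0.6×48 ≈ 29 and 0.3×48 ≈ 14. Then p = 0.005 and X = 5 in each arm (4 and 4 with correction). The missing-only grid, uncorrected, tips in 0 of 16 combinations at m = 3, 3 of 49 at m = 6 and 86 of 289 at m = 16. Missingness has moved X from 9 and 8 to 5 and 5, but only by lowering the counts.

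**Step 4: what vehicle X means.** The test sees only counts, so it does not matter which vehicle non-responder is flipped. With CSB-001 fixed, the vehicle half traces the i = 0 row of the grid, and its X = 8 in Step 1 equals the first tipping point on that row whenever at least 8 vehicle outcomes are missing. It is informative only when set beside the number imputed.

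**Step 5: Week 8 healing.** Read literally, SAP 7.4 leaves missing Week 8 outcomes unimputed for the secondary endpoint. If such subjects drop out of that table, both halves of the tipping point in SAP 9.2 change observed outcomes only.

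**The case against.** The best defense is that the vehicle half already contains the most adverse scenario: missing vehicle subjects healed, missing CSB-001 subjects not. That is correct. Raising i only helps CSB-001: for 38/64 v 19/64, the j needed to tip rises 8, 9, 10, 11, 13 as i goes from 0 to 4. If vehicle X exceeds the number of vehicle outcomes imputed, the worst case cannot overturn the result. Varying the arms one at a time is therefore a minor matter. What remains is that the SAP does not call for the comparison that gives X this meaning, and that the CSB-001 half has no such reading.

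A reader might go further in four ways that the documents do not support:

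- **That only observed outcomes are flipped.** For the primary endpoint this is true of the CSB-001 arm alone; vehicle non-responders include imputed ones.
- **That the answer is the same at 0% and 25% missing.** This holds only for a fixed 2x2 table (Step 3).
- **That the non-responder rule is never stressed.** The completers and LOCF analyses both replace it. Each is one fixed alternative, however, and neither shows how many missing vehicle healers would overturn the result.
- **That 16 imputed outcomes per arm is the planned rate.** SAP 5.0 states about 10% dropout plus an unquantified image risk, and SAP 6.1 removes from the full analysis set subjects who are not stage 2 or 3 per the CRC or have no post-baseline image. Those subjects are not imputed.

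At about 10% missing (6 of 64, leaving 58), the assumed counts are 0.6×58 ≈ 35 and 0.3×58 ≈ 17. Vehicle X is then 7, above the 6 missing, and the worst case 35 v 23 stays significant uncorrected (p=0.033). With correction X is 6 and the worst case just fails (p=0.051). The danger at the stated dropout rate is therefore modest, and this is one added sensitivity analysis that alters no primary decision.

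**Conclusion.** The point holds in limited form. Item 3 of SAP 9.1.2 is presented as missing-data sensitivity but is a fragility count. Its CSB-001 half tests no missing-data assumption. Its vehicle half yields the right number for the most adverse case but is neither capped at nor compared with the number of vehicle outcomes imputed. The consequence is a possible misreading of robustness, not an error in the primary analysis.

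For scale, X = 9 and 8 on 38/64 v 19/64 (8 and 7 with correction) is compatible with no loss of significance at 6 missing per arm and with loss in 40 of 289 combinations at 16. These figures rest on assumed result tables, equal missingness in the two arms, all 64 per arm staying in the full analysis set, and an uncorrected test in the grid. They show how the procedure behaves and do not predict the trial's result.

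**What to change.** Rewrite item 3 so that reclassification is limited to subjects whose primary outcome was imputed, and leave observed CRC outcomes unchanged. A subject whom the CRC read as not healed at Week 8 has an observed outcome and should not be counted as imputed merely for lacking a Week 10 visit. Then:

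1. Report the number imputed in each arm, mA (CSB-001) and mV (vehicle).
2. Rerun the primary test for every i from 0 to mA and j from 0 to mV counted as responders, and show the boundary where p crosses 0.05.
3. Report the worst case, i = 0 and j = mV.
4. State whether the chi-squared test is continuity-corrected.
5. If the present procedure is kept, label it a fragility count and move it out of the missing-data list.

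Apply the same to Week 8 CRC healing in SAP 9.2, and state how subjects with missing Week 8 readings enter that table, given SAP 7.4.

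The cost is SAP wording and a short program. No new data are needed, and the primary analysis is unchanged.
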